7.2.3 Follow-up Period

The following assessments and procedures should be performed during the Follow-up Period. Not all of the assessments and procedures listed below are to be performed at every scheduled

visit. For the timing of when to administer individual assessments and procedures, see the Schedule of Assessments in [Table 1, Section 7.1](#).

Corticosteroid Dose Record

The patient's steroid dosing for the treatment of aGvHD must be documented on the Corticosteroid Dosage Form of the eCRF. Dosages will be recorded as is (average daily dose is acceptable). Methylprednisolone equivalence will be calculated later.

Physical Examination

A qualified health-care professional will give each patient a complete physical examination to document any changes in the general health of the patient by organ system. Patient height and weight will also be recorded.

Local Laboratory Analyses

Laboratory assessments will be performed through a local laboratory. Clinically significant laboratory abnormalities should be recorded as AEs according to the Principal Investigator's judgment. Blood samples may be obtained through standard venipuncture technique or through a venous access catheter, according to institutional guidelines.

Blood will be collected and processed for the following:

- Total bilirubin, to be used for the weekly assessment of aGvHD status.
- CBC with differential (WBC, platelets, hemoglobin, hematocrit, neutrophils, lymphocytes, basophils, eosinophils, and monocytes) and an absolute neutrophil count.
- Electrolyte panel (sodium, potassium, chloride, bicarbonate, BUN, creatinine, and glucose), BUN/creatinine ratio, calcium, phosphorous, and magnesium.
- AST, ALT, GGT, total bilirubin, direct bilirubin, indirect bilirubin, alkaline phosphatase, and lactate dehydrogenase.

Any laboratory test results that are needed to manage aGvHD or other medical conditions should be drawn outside this schedule as clinically indicated.

Assessment of aGvHD Status

Patients will be evaluated by the treating physician for the presence or absence of aGvHD manifestations of the skin, liver, and gut. Source data will be collected for each patient and entered into the eCRF, and a scoring algorithm will be applied to calculate the grade of aGvHD using the modified IBMTR Severity Index and the modified Glucksberg criteria.

Skin aGvHD Staging

Only active rash (erythema) is considered in body surface area (BSA) calculations. Hyper- (e.g., brown/tanned rash) or hypopigmentation representing post-inflammatory changes are not included in the BSA assessment. Skin involvement will be reported as % BSA using the Rule of Nines ([Appendix G: Percent Body Surface Area Assessment](#)) and/or presence of bullae.

Other common etiologies for skin symptoms include drug rash, conditioning regimen toxicity, infection, and cytokine storm/engraftment syndrome.

Liver aGvHD Staging

Bilirubin will be determined from a single blood sample. Total bilirubin (not direct/conjugated) will be used for staging.

Other common etiologies for liver symptoms include drug toxicity, conditioning regimen toxicity, veno-occlusive disease, total parenteral nutrition, cholestasis, and infection.

Gut aGvHD Staging

Stool output will be reported as volumes for all inpatients and as episodes (frequency and consistency) for all outpatients. Patients weighing ≥ 50 kg will be graded using total stool volume per day (mL/day), while patients weighing < 50 kg will be evaluated for gut symptoms according to mL/kg/day, as a function of body weight.

For patients who weigh < 50 kg, every effort should be made to collect stool volumes as a daily average in milliliters over a 3-day period. For diarrhea volumes, report liquid stool volume in the following order:

1. Average of 3 consecutive days, if available.
2. Otherwise, the 3 days closest to each other within 1 week.
3. Otherwise, the average of 2 consecutive days.
4. Otherwise, the maximum volume from the isolated day(s) available.

Formed or mostly formed stools should not be quantified or counted in the estimation of liquid stool volume. It will be noted on the source document, if urinary mixing is present. For patients in diapers, the volume will be calculated from the weight of the diaper before and after use. For outpatients, Patient Stool Volume Records will be provided, according to usual site practice, along with instructions for collection and measurements. Stool volume collection should be done without regard to the ECP treatment schedule.

When diarrhea is reported as episodes instead of individual volumes, episodes of non-quantified liquid stool will be counted as 200 mL each for patients ≥ 50 kg and 4 mL/kg for patients < 50 kg.

When gross blood is present:

- Bloody diarrhea is staged as 4, even if low volume.
- Blood-streaked low volume (< 500 mL/day or < 10 mL/kg/day) stools (as can be seen with bleeding hemorrhoids, for example) are staged as 0.

For stage D or stage 4 gut involvement, severe pain is defined as:

- Pain that requires the start of narcotic use, or an increase in on-going narcotic use PLUS.
- Pain that significantly impacts performance status, as determined by the treating physician.

Other common etiologies for GI symptoms include drug toxicity, conditioning regimen toxicity, and infection.

Upper GI aGvHD Staging

The determination that nausea, vomiting and/or anorexia are persistent is based on clinical judgment. As a general rule, nausea lasting fewer than 3 days, fewer than 2 vomiting episodes per day for at least 2 days, and anorexia without weight loss should not be considered persistent.

Other common etiologies for upper GI symptoms include drug toxicity, conditioning regimen toxicity, infection, and total parenteral nutrition.

Concomitant Medications

All concomitant medications taken by patients, including those medications taken between visits, will be recorded on the Prior and Concomitant Medication Report Form of the eCRF.

Adverse Events

Patients will be asked about AEs that may have occurred after the patient signed and dated the ICF. Each patient will be asked about AEs using the non-specific question, “How have you been since your last visit?” Any AEs elicited by this question will be recorded on the Adverse Event Report Form of the eCRF, as well as any AEs spontaneously volunteered by the patient or observed by the study staff.

Nonrelapse Mortality

Nonrelapse mortality is defined as death due to any cause, with death due to relapse as a competing risk [Das-Gupta et al., 2014b].

Survival

Recipient Death Information must be entered into the eCRF within 24 hours of knowledge a patient’s death. Once the cause of death is determined, the information must be recorded in the eCRF. Passive follow-up (chart review) will be performed to assess survival at Week 26.

7.2.4 Early Study Termination Visit

End of study assessments (Schedule of Assessments in [Table 1, Section 7.1](#)) will be completed for those patients who discontinue ECP, prior to completing 12 weeks of treatment, and will not remain in the study. The Early Study Termination page of the eCRF must be completed for these patients, with the reason for withdrawal from the study. For those patients who terminate early, every effort should be made to perform the early termination assessments.

8. SAFETY PARAMETERS

8.1 ADVERSE EVENTS

8.1.1 Collection of Adverse Events

It is the responsibility of the Principal Investigator to collect all AEs (both serious and nonserious) derived by spontaneous, unsolicited reports of patients, by observation, and by routine open questionings (e.g., “How have you felt since I last saw you?”).

8.1.2 Definitions

An AE is any untoward medical occurrence that occurs in a patient or clinical investigation patient administered a pharmaceutical product or an investigational medicinal product, and does not necessarily have to have a causal relationship with this treatment. An AE can therefore be any unfavorable and unintended sign (including an abnormal laboratory finding), symptom, or disease temporally associated with the use of an investigational product, whether or not considered related to the product. Adverse events will be graded according to the Common Terminology Criteria for Adverse Events (CTCAE), version 4.0 and will be coded using MedDRA based on the verbatim term collected in the eCRF.

All AEs, including intercurrent illnesses, occurring during the study will be documented in the eCRF. Underlying disease, hospitalization for the study purpose, and abnormal laboratory results associated with an underlying disease will not be considered AEs. Relapse of underlying malignancy will not be considered an AE or serious AE (SAE) but will be captured and analyzed separately. Underlying disease will not be considered an AE unless it meets any of the seriousness criteria—in particular, hospitalization and deaths. Concomitant illnesses that existed before entry into the study will not be considered AEs unless they worsen during the treatment period. Pre-existing conditions will be recorded in the eCRF on the Medical History or appropriate page. Adverse events will be captured from the time of ICF signing until completion of the study (Week 16) or early cessation of treatment for any reason.

The underlying disease is defined as:

1. Clinical disease that was the reason for the bone marrow or stem cell transplant (e.g. malignancy, immunodeficiency disorder, Sickle Cell Disease, etc).
2. Typical, expected clinical manifestations of patients who have received bone marrow transplant or stem cell transplant.
3. Typical, expected clinical manifestations of patients with acute graft-vs-host disease.

The following signs, symptoms, laboratory results, and diseases are considered AEs:

1. Signs and symptoms not related to the underlying disease.
2. Signs and symptoms not typical following bone marrow transplant or stem cell transplant.
3. Abnormal laboratory results not related to the underlying disease that are clinically significant (expert clinical judgment required by the investigator to assess if an abnormal laboratory result is clinical significant/not clinically significant).

4. Underlying disease that worsens and meets criteria for a SAE during the study.
5. Concomitant illnesses that existed before entry into the study that worsen during the treatment period.
6. Death due to any cause.

The following signs, symptoms, laboratory results, diseases are not considered an AE:

1. Underlying disease that does not meet criteria for being a serious AE (see [Section 8.1.3.1](#)).
2. Hospitalization related to study enrollment procedures, treatments, etc.
3. Hospitalization for elective or planned procedure to treat a preexisting condition that has not worsened and does not result in another serious outcome (e.g. death, hospital prolongation, etc).
4. Abnormal laboratory results associated with the underlying disease (as determined by expert clinical judgment of the investigator).
5. Concomitant illnesses that existed before entry into the study that do not worsen during the treatment period.

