
Study design
	
This is a single-arm, open-label, multicenter study of the efficacy of UVADEX (methoxsalen) Sterile Solution in conjunction with THERAKOS CELLEX Photopheresis Systems in pediatric patients with steroid-refractory aGvHD. The study is composed of Screening, Treatment, and Follow-up Periods.
 
Screening:
 
After the informed consent/assent form (ICF) is signed, the screening assessments will be performed in a single visit to establish the eligibility of the patient, based on inclusion and exclusion criteria, as well as aGvHD grading. Scheduling of the first week of ECP treatments and the arrangements for availability of typed and cross-matched donor packed red blood cells (PRBCs) for transfusion, if required, will be made in advance of patients entering the Treatment Period.
 
Treatment Period:
 
Once eligibility is established, patients will enter the 12-week ECP Treatment Period. The availability of typed and cross-matched donor PRBCs for transfusion during treatment, if needed, should be established prior to the scheduling of ECP treatments.
 
Patients will be allowed to continue standard aGvHD prophylaxis regimens (e.g., cyclosporine, tacrolimus, methotrexate, mycophenolate mofetil) without the addition of new therapies. Patients will be allowed to discontinue prophylaxis regimens for reasons of toxicity, and will also be allowed to switch to another prophylaxis medication within the same class (e.g., the calcineurin inhibitors cyclosporine and tacrolimus) for reasons of toxicity.
 
All patients enrolled in this trial will have received corticosteroids for the treatment of aGvHD. After entering the treatment period on study, it is suggested that the steroid dose be decreased by 12.5% to 25% of the dose after the initiation of ECP therapy if a sustained response of aGvHD has been observed for at least 3 consecutive days. The suggested goal is to have decreased the starting steroid dose by at least 50% at 4 weeks after initiation of ECP.
 
Special Warnings and Precautions for Use
 
Patients should be explicitly instructed to wear ultraviolet A (UVA)-absorbing, wrap-around sunglasses and cover exposed skin or use a sunblock (SPF 15 or higher) for the 24 hour period following treatment with methoxsalen, whether exposed to direct sunlight, or indirect sunlight through a glass window.

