7.2 STUDY ASSESSMENTS AND PROCEDURES

7.2.1 Screening Period

The Screening Period begins once a patient signs the ICF, and will consist of at least one screening visit. If a patient does not meet the eligibility criteria, the patient will be considered a “screening failure” and will be discharged from the study. A small set of eCRF pages (i.e., a “Screening Failure Packet”) will be completed for those patients who are not eligible for this study.

Informed Consent/Assent

Patient consent/assent must be obtained before a patient’s participation in ANY study-related procedures. A copy of the signed and dated ICF will be given to the patient, legal guardian or legally authorized representative. The original signed and dated ICF will be maintained at the study site. The date(s) of signed consent must be recorded in the eCRF. For more information, see [Section 10.7 Informed Consent/Assent](#).

Inclusion/Exclusion Criteria

The inclusion and exclusion criteria MUST be assessed for patient eligibility at screening and recorded on the Inclusion Criteria and Exclusion Criteria Forms of the eCRF. Patients who do not meet the inclusion and exclusion criteria will be considered “screening failures” and will be discharged from the study.

Focused Medical History

The medical history should include any medical condition that the patient recalls or that is part of the medical record that is relevant to the condition under study. Any condition present at the onset of the study should be noted. Any condition NOT listed on the Medical History and Review of Symptoms Form of the eCRF will be considered an AE if it occurs during the course of the study (i.e., any time after the patient has signed the ICF). Any condition that increases in frequency or worsens as compared to the Medical History and Review of Symptoms Form of the eCRF will also be considered an AE.

Transplant History

Background information about a patient’s transplant (e.g., date of transplant, type of bone marrow transplant, underlying condition [malignant or non-malignant]) will be recorded on the Transplant History Form of the eCRF.

Corticosteroid Dosing History

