When gross blood is present:

- Bloody diarrhea is staged as 4, even if low volume.
- Blood-streaked low volume (< 500 mL/day or < 10 mL/kg/day) stools (as can be seen with bleeding hemorrhoids, for example) are staged as 0.

For stage D or stage 4 gut involvement, severe pain is defined as:

- Pain that requires the start of narcotic use, or an increase in on-going narcotic use PLUS.
- Pain that significantly impacts performance status, as determined by the treating physician.

Other common etiologies for GI symptoms include drug toxicity, conditioning regimen toxicity, and infection.

Upper GI aGvHD Staging

The determination that nausea, vomiting and/or anorexia are persistent is based on clinical judgment. As a general rule, nausea lasting fewer than 3 days, fewer than 2 vomiting episodes per day for at least 2 days, and anorexia without weight loss should not be considered persistent.

Other common etiologies for upper GI symptoms include drug toxicity, conditioning regimen toxicity, infection, and total parenteral nutrition.

ECP Treatments

Patients should be scheduled to receive the first ECP treatment as soon as possible upon confirmation of eligibility. Patients must be enrolled and receive their first ECP treatment within 1 week (7 days) after being diagnosed as having steroid-refractory aGvHD. Week 1 (7 days) begins on the day the first ECP treatment is received (Day 1 of Week 1). The availability of typed and cross-matched donor PRBCs for transfusion during treatment, if needed, should be established prior to the scheduling of ECP treatments.

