8.1.4 Recording Adverse Events

Adverse events will only be recorded from ICF signing until Week 16. Following Week 16 there will be a passive chart review which will not include the collection of AEs. Any AEs occurring after the end of the study should be reported to the Sponsor by the Investigator if the Principal Investigator considers that there is a causal relationship with the study treatment.

All AEs (including AEs resulting from active standard of care medication and study device), regardless of the relationship to study drug, will be recorded in the eCRF. In addition, the technician performing the ECP procedure will observe and record any AEs that occur during the procedure. Treatment will be stopped if the patient cannot tolerate the procedure.

All AEs recorded in the eCRF should contain a brief description of the event, date of onset, date of resolution, intensity, treatment required, relationship to study drug(s) and/or device, action taken with the study drug and/or device, outcome, and whether the event is classified as serious.

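### Section 8.1.2 limits worsening of a pre-existing illness to the 12-week treatment period, which contradicts section 7.2.1 and is narrower than the AE collection window

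*Combined protocol and SAP*

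**What the plan says.** Section 8.1.2 states the rule for concomitant illness three times:

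- In the paragraph: "Concomitant illnesses that existed before entry into the study will not be considered AEs unless they worsen during the treatment period".
- Item 5 of the list of what counts as an AE: "Concomitant illnesses that existed before entry into the study that worsen during the treatment period".
- Item 5 of the list of what does not: "Concomitant illnesses that existed before entry into the study that do not worsen during the treatment period".

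The treatment period is a defined part of the study. The synopsis separates Screening, Treatment and Follow-up and says that "patients will enter the 12-week ECP Treatment Period". Section 7.2.2 starts Week 1 on the day of the first ECP, and Table 1 places Week 16 under Follow-up.

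Other text is wider. Section 7.2.1 (Focused Medical History) makes an AE of "Any condition that increases in frequency or worsens as compared to the Medical History and Review of Symptoms Form". Section 8.1.4 says "Adverse events will only be recorded from ICF signing until Week 16". The capture sentence in 8.1.2 gives the same span but adds early cessation of treatment as an alternative end.

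Underlying disease has its own rule. Item 1 of the not-an-AE list excludes "Underlying disease that does not meet criteria for being a serious AE", so serious underlying disease counts. Item 4 of the AE list applies that test over the whole study, not only the treatment period.

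**The concern.** The definition of an AE should cover at least the period over which AEs are collected. Here it does not, for one class of event. Taken literally, 8.1.2 tells a site that a pre-existing illness worsening in Week 14, or after consent but before the first ECP, is not an AE. Section 7.2.1 tells the same site that it is.

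The population makes this more than a drafting matter. Eligibility excludes only uncontrolled infection and allows creatinine up to twice the upper limit of normal, so patients can enter with illnesses that may worsen. They may also continue ECP on commercial product after Week 12, so Weeks 13-16 can include continuing exposure. Safety is a secondary objective, and section 5.1.1 says that UVADEX safety is not established in children. With a single arm, there is no control group to offset uneven classification between sites. The DSMB reviews SAEs and the most frequent AEs, so any inconsistency would reach it as well as the final report.

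**Working it through.** The plan gives no statistical figure to reproduce. The check compares time windows and rules.

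**Windows**

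- Treatment period: Weeks 1-12 from the first ECP (synopsis; 7.2.2).
- AE collection: consent to Week 16 (8.1.2 and 8.1.4).
- Late gap: 16 − 12 = 4 weeks (Weeks 13-16). As a share of the time from first ECP to Week 16: 4/16 = 25%.
- Early gap: consent to first ECP. No length is stated. Section 7.2.2 requires the first ECP within 7 days of the refractory diagnosis. Assuming consent on or after that diagnosis, the gap is 0-7 days.

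**How each provision treats worsening outside the treatment period**

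| Provision | Result |
|---|---|
| 8.1.2, paragraph and both item 5 entries | Not an AE |
| 7.2.1, Focused Medical History | AE; the sentence on worsening has no time limit |
| 8.1.2, AE list item 1 (signs and symptoms unrelated to underlying disease) | Could count as an AE; no period limit |
| 8.1.2, AE list item 4 (underlying disease) | AE if serious, at any time in the study; a different class of illness, but a different window from the item next to it |
| 8.1.2, not-an-AE list item 3 (planned hospitalization for a pre-existing condition) | Exempt only if the condition has not worsened; no period limit |
| 8.1.2, AE list item 6 | Every death is an AE |
| 8.1.3.1 | An SAE is any untoward occurrence meeting a seriousness criterion; all must be reported whatever the cause |
| 7.2.3, laboratory and AE paragraphs | Clinically significant laboratory abnormalities are recorded as AEs; patients are still asked about AEs in follow-up |
| 8.1.4 | Sets when AEs are recorded, not what counts as one |

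**Reading them together**

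1. 8.1.2 and 7.2.1 give opposite answers for the same event. That is a direct contradiction.
2. 8.1.2 and 8.1.4 do not contradict each other in that sense. The definition is narrower than the recording window, and 8.1.2's own capture sentence shows the same mismatch.
3. By severity: deaths are always captured. Non-fatal serious worsening is excluded by item 5 but must be reported under 8.1.3.1. Non-serious worsening has no such backstop and depends on which section the site follows.

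**Scale.** With 48 patients, reclassifying one patient moves an incidence by 1/48 = 2.1 percentage points. The documents give no rate for late worsening of pre-existing illness, so the number of affected events cannot be estimated.

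**The case against.** The strongest reply is that little would be lost. Section 7.2.1 already makes the worsening an AE, sites ask about AEs at Week 16, and significant laboratory changes are recorded separately. The follow-up panel includes creatinine and BUN, so worsening renal function has a clear route. Section 8.1.2 also defines underlying disease broadly enough to take in typical manifestations of transplant and of aGvHD, so much comorbidity may fall under that separate rule. What remains is mainly non-serious, non-laboratory worsening of unrelated illness. All of this stands as a limit on the size of the problem. It does not remove the contradiction: a site that follows the explicit not-an-AE list will omit what a site following 7.2.1 records.

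A reader might go further and infer that such worsening is dropped altogether, or that a serious case, not being an AE, cannot be an SAE. The documents do not support either inference. Section 8.1.3.1 defines an SAE directly from any untoward medical occurrence and requires all-cause reporting, deaths are listed without a time limit, and the routes above remain open. What can fairly be said about serious cases is narrower. Item 5 has no seriousness exception of its own, and 8.1.3 is introduced as an assessment of each AE. A site that has already ruled an event out under item 5 might therefore not go on to assess seriousness.

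It is also tempting to read 25% as the share of AEs lost, or to claim a known downward bias in post-treatment safety. The figure is a share of calendar time, and the documents contain no event rate to support either statement.

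**Conclusion.** The point holds as an internal inconsistency in AE ascertainment. Section 8.1.2 conflicts with 7.2.1 on worsening of pre-existing concomitant illness and is narrower than the collection window in 8.1.2 and 8.1.4. It affects Weeks 13-16 and the interval from consent to first ECP. The consequence is possible inconsistent classification between sites, chiefly of non-serious worsening. Non-fatal serious worsening is under two conflicting instructions, which should not be left open where reporting is due within 24 hours.

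The conclusion rests on reading the treatment period as the defined 12 weeks. The 0-7 day figure further assumes that consent does not precede the refractory diagnosis. The number of events affected is unknown. The correction is worth making because it is specific and nearly free, not because a large loss of data has been shown.

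**What to change.** In section 8.1.2:

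1. In the paragraph and in item 5 of both lists, replace the treatment-period limit with *during the AE collection period (from ICF signing to Week 16)*.
2. In the same three places, use the 7.2.1 criterion: *worsens or increases in frequency*.
3. Add a sentence saying that item 5 does not override SAE reporting under section 8.1.3.1.
4. Reconcile the early-cessation end-point in 8.1.2 with 8.1.4, which has no such alternative. Otherwise step 1 leaves a new mismatch for patients who stop ECP early.

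Do not add a seriousness exception to item 5 itself. It could turn a stable, unworsened illness, such as one with an existing disability, into an AE. Step 3 meets the need without that side effect.

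The cost is a few wording changes and a line in the eCRF completion guide. AE counts may rise slightly. There are no extra visits, and the primary endpoint, alpha and power are unchanged.

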6.6 EARLY CESSATION OF STUDY PARTICIPATION

If the Principal Investigator, the Sponsor, or the Medical Monitor becomes aware of conditions that suggest a risk to safe participation in the study, study treatment will be discontinued. If the Principal Investigator, based on his/her medical judgment, determines there is a risk to the patient with continued participation in the study, the patient will be withdrawn. The study may also be terminated early for all patients at the Sponsor's discretion. Conditions that may warrant termination include, but are not limited to:

- The discovery of an unexpected, significant, or unacceptable risk to the patients enrolled in the study.
- Failure to enroll patients at an acceptable rate.
- A decision on the part of the Sponsor to suspend or discontinue development of the drug.
- Recommendation by the Data Safety Monitoring Board (DSMB).

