6.6.1 Early Cessation of Study Treatment

Patients *may* voluntarily stop receiving therapy at any time. The patient's legal guardian/legally authorized representative may choose to stop a patient's therapy at any time.

If a patient voluntarily ceases to receive therapy, the primary reason must be requested and, if provided, will be recorded on the Study Termination page of the eCRF.

The Principal Investigator and/or the Sponsor may also judge that early cessation of treatment is warranted for any one of the following reasons:

- Occurrence of AEs that pose a risk to safe participation.

- Abnormal laboratory value(s) that pose a risk to safe participation.
- Abnormal test procedure result(s) that pose a risk to safe participation.
- Unsatisfactory therapeutic effect.
- Condition no longer requires treatment.
- Significant protocol deviation.
- Patient non-compliance with protocol requirements.

Unless a patient/legal guardian/legally authorized representative withdraws study consent, patients will continue to be followed as per the trial protocol and clinical assessment schedule to ensure that full, intent-to-treat follow-up data are obtained.

For patients who are lost to follow-up, the Principal Investigator should show due diligence by documenting in the source documents steps taken to contact the patient (e.g., dates of telephone calls, emails).

Patients who voluntarily cease to receive treatment early will not be replaced. Patients will be replaced if they are enrolled in the trial but are not treated.

If a patient has received any ECP treatments and is administered a second-line therapy other than ECP for the treatment of aGvHD, or discontinues study treatment, that patient will be considered a nonresponder and may not be replaced.

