7. STUDY CONDUCT

7.1 SCHEDULE OF ASSESSMENTS

Table 1. Schedule of Assessments

Assessments and Procedures	Screening	Treatment Period, weeks (+/- 2 days)												Follow-Up Period, weeks		Early Study Termination
		1	2	3	4 (Day 28) Primary Endpoint	5	6	7	8 (Day 56) Secondary Endpoint	9	10	11	12 (Day 84) Secondary Endpoint	16	26	
Informed consent/assent form	X															
Inclusion/exclusion criteria	X															
Focused medical history	X															
Transplant history	X															
Corticosteroid dosing	X	X	X	X	X	X	X	X	X	X	X	X	X	X		X
Complete physical examination	X				X				X				X	X		X
Targeted physical examination		X	X	X		X	X	X		X	X	X				
Urine Pregnancy test ^a	X	X	X	X	X	X	X	X	X	X	X	X	X			X
Vital signs	X	X	X	X	X	X	X	X	X	X	X	X	X	X		X
Lansky Performance Status	X				X				X				X	X		X
Local laboratory analyses ^b	X	X	X	X	X	X	X	X	X	X ^h	X	X	X	X		X
Assess aGvHD status ^c	X	X	X	X	X	X	X	X	X	X	X	X	X ⁱ	X		X
Baseline total bilirubin level and aGvHD assessment ^d		X														
Total bilirubin level and primary endpoint aGvHD status assessment ^e					X											
Total bilirubin level and secondary endpoint aGvHD status assessment ^f									X				X			
Number of ECP treatments ^g		3	3	3	3	2	2	2	2	2	2	2	2			

Concomitant medications	X	X	X	X	X	X	X	X	X	X	X	X	X	X	X	X
Adverse events	X	X	X	X	X	X	X	X	X	X	X	X	X	X	X	X
Nonrelapse mortality		X	X	X	X	X	X	X	X	X	X	X	X	X	X	X
Survival		X	X	X	X	X	X	X	X	X	X	X	X	X	X	X
Early study termination ^j																X

^a If the result of the urine test is positive, blood must be drawn for a serum human chorionic gonadotropin (HCG) level and analyzed locally. A serum test may be performed in place of the urine test.

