^j Early study termination applies to only to those patients who discontinue ECP prior to 12 weeks of treatment and do not remain on the study.

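### Section 8.1.2 also ends adverse event capture when ECP stops early, in conflict with Section 8.1.4, the synopsis and Section 6.6.1

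*Combined protocol and SAP*

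**What the plan says.** Section 8.1.2 gives the AE window as consent "until completion of the study (Week 16) or early cessation of treatment for any reason". Earlier in the same paragraph it says: "All AEs, including intercurrent illnesses, occurring during the study will be documented in the eCRF".

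Section 8.1.4 gives a different window: "Adverse events will only be recorded from ICF signing until Week 16". The synopsis (Study assessments, Adverse Events) repeats that sentence. Neither mentions treatment cessation.

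Section 6.6.1 deals with patients who stop treatment. Unless consent is withdrawn, "patients will continue to be followed as per the trial protocol and clinical assessment schedule".

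Two places separate stopping ECP from leaving the study. Footnote j of Table 1 reserves the early study termination column for "those patients who discontinue ECP prior to 12 weeks of treatment and do not remain on the study". Section 7.2.4 provides the termination assessments "for those patients who discontinue ECP, prior to completing 12 weeks of treatment, and will not remain in the study".

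**The concern.** The protocol states two end points for AE capture. They coincide for a patient who completes ECP. They diverge for a patient who stops ECP and remains in the study, a group that footnote j and Section 7.2.4 recognise. A site following Section 8.1.2 to the letter would stop recording that patient's AEs on the day ECP ended. A site following Section 8.1.4 would continue to Week 16.

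AEs are a listed secondary endpoint (Section 3.2.2), and Section 5.1.1 acknowledges that safety in children is not yet established. The affected group is also selected: the reasons for cessation in Section 6.6.1 include AEs and abnormal laboratory values that make continued participation unsafe. Non-serious AE recording could therefore differ between sites, and between patients who stop early and those who complete.

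**Working it through.** The plan gives no figure to reproduce, so the check is a comparison of text followed by one subtraction.

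**Does AE capture continue after ECP stops, in a patient still on study?**

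| Place | Reading |
|---|---|
| 8.1.2, capture window | No: ends at cessation of treatment |
| 8.1.2, earlier sentence in the same paragraph | Yes: all AEs during the study |
| 8.1.4 | Yes: to Week 16 |
| Synopsis, Adverse Events | Yes: to Week 16 |
| 6.6.1 | Yes by implication: follow-up continues on the assessment schedule |
| Table 1, AE row | Yes: every treatment week and Week 16; as extracted, also Week 26 |

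Among the passages on AE recording, only the one clause in 8.1.2 stops capture with treatment. Table 1 supports continued capture but does not confirm the Week 16 limit. As extracted, its AE row is marked in all 16 columns, including Week 26, whereas Section 8.1.4 and the synopsis exclude AE collection after Week 16. Table conversion may explain that mark.

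**Weeks of capture lost per patient under the literal wording.**

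Inputs: Week 1 starts with the first ECP treatment (Section 6.2.1), and AE recording runs to Week 16 (Section 8.1.4). Let *s* be the last week of ECP for a patient who then stays on study to Week 16. The screening interval after consent is unaffected and is not counted.

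Weeks lost = 16 − *s*; share of the window = (16 − *s*)/16.

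- *s* = 2: 16 − 2 = 14 weeks; 14/16 = 87.5%
- *s* = 4: 16 − 4 = 12 weeks; 12/16 = 75%
- *s* = 8: 16 − 8 = 8 weeks; 8/16 = 50%

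These are weeks of recording, not events. Sections 8.1.2 and onward exclude non-serious typical manifestations of transplant and of aGvHD from the AE definition, and events during the ECP procedure occur before stopping. The share of events lost may therefore be smaller than the share of weeks.

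**Trial level.** The total would also need the proportion who stop early, when they stop, how many stay on study, and how many sites follow 8.1.2 literally. The documents give none of these, so no total is computed.

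**The case against.** The strongest reply is that the clause is loose wording for leaving the study. Study completion or early cessation reads naturally as two ways in which participation ends, and the protocol blurs the terms elsewhere. The section headed "6.6 EARLY CESSATION OF STUDY PARTICIPATION" opens by discontinuing treatment, and Section 6.6.1 puts the reason for stopping therapy on a study termination form. The clause also sits in a definitions section, while the section on recording AEs, the synopsis and the visit instructions in 7.2.2 and 7.2.3 contain no such cut-off. Many sites would probably record to Week 16. This is why the point is a reconciliation and not a major fault. It does not remove the conflict: the clause says treatment, and footnote j and Section 7.2.4 show that the protocol distinguishes treatment from study where it needs to.

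A second reply is that Section 6.6.1 cannot settle the matter alone, because it continues follow-up according to the protocol. In addition, the synopsis (Dosage and frequency of administration) and Section 7.2.2 (Assessment of aGvHD Status) run weekly aGvHD evaluation to Week 12 or to the visit at which treatment ends, if earlier. This stands. It leaves unclear which weekly contacts continue after ECP stops, so the loss is stated in weeks and not in scheduled contacts.

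A reader might infer that serious events or deaths would be missed. The documents do not support that. Section 8.1.3.1 requires any serious event during the investigation to be reported, Section 8.1.6 follows such events to resolution or another defined end, and Sections 7.2.2 and 7.2.3 require death information in the eCRF. The text of Section 8.1.5 was not available to check. Section 8.1.4 also asks for causally related AEs after the end of the study to be reported to the sponsor, but that rule does not clearly cover the interval between stopping ECP and Week 16 in a patient who is still on study.

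**Conclusion.** The inconsistency is real and should be corrected. Under the literal wording, a patient who stops ECP and stays on study to Week 16 loses 14, 12 or 8 of 16 weeks of mainly non-serious AE capture, for stopping after Week 2, 4 or 8. This rests on two conditions: the site follows 8.1.2 over 8.1.4, and the patient remains in the study.

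A reader might go further and put a percentage on the AE data lost across the 48 patients. That would rest wholly on assumed stopping rates and site behaviour, so no such figure is offered. Nor does the point touch the primary result: Section 9.3.1 counts a patient who discontinues study treatment as a nonresponder, and that rule does not depend on AE records.

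**What to change.** In Section 8.1.2, delete the early-cessation limb of the capture window. State instead that AEs are captured from consent to Week 16 in every patient who remains in the study, whether or not ECP has stopped. For patients who leave the study, capture should run to the early termination visit or, if there is none, to the date of withdrawal, death or last contact. That fallback is needed because Section 7.2.4 asks sites to try to perform the termination assessments but cannot guarantee them.

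At the same time:
- reconcile the Week 26 mark in the Table 1 AE row with the Week 16 limit in Section 8.1.4 and the synopsis, after checking it against the formatted table;
- reconcile the wording in the synopsis and Section 7.2.2 that ends weekly aGvHD evaluation when treatment stops with the continued follow-up in Section 6.6.1.

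Leave the serious event reporting rules unchanged, and check Section 8.1.5 for consistency with the revised window.

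The cost is small: a short amendment to the text, and AE entry for the added patient-weeks, for example 12 weeks for a patient who stops after Week 4 and stays to Week 16.
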